## 12.8 Efficacy Analyses

### 12.8.1 Primary Efficacy Analyses

For each of the co-primary efficacy endpoints, proportion of subjects who achieved PASI-75 and IGA success at Week 24, will be tested to compare the difference between the subjects treated with PPC-06 and placebo, separately. To provide sufficient evidence of treatment effect, both PASI and

IGA based response rate must be rejected at the same significance level. The hypothesis testing for the three dose groups will be conducted sequentially from high to low dose; therefore, the 2-sided Type I error rate remains at the 0.05 level.

The primary efficacy analyses will be based on the FAS population using MI. Each multiple imputed dataset will be analyzed using a logistic regression model with treatment group, baseline BMI, and pooled analysis center as factors. The primary treatment comparisons will be the contrasts between the PPC-06 doses and placebo. The estimates and standard errors (SEs) of the log (odds ratio) based on the 50 imputed datasets will be combined by applying Rubin's rules for multiple imputed datasets. The combined log (odds ratio), odds ratio and associated 95% CI, and the resulting p-value will be provided. SAS Proc MI, Proc LOGISTIC, and Proc MIANALYZE will be utilized for these analyses. The averaged proportion of PASI-75 responders and IGA Success Rates over the 50 imputed datasets will also be presented.

Sensitivity analyses will be conducted using m-NRI and LOCF, following a same method as described above for each multiple imputed dataset. For each of the co-primary efficacy endpoints, proportion of subjects who achieved PASI-75 and IGA success at Week 24, will be tested to compare the difference between the subjects treated with PPC-06 and placebo, separately. PASI-75 and IGA Success Rates will be analyzed using a logistic regression model with treatment group, baseline BMI, and pooled analysis center as factors. The odds ratio between each PPC-06 group and placebo, along with the 95% CI and p-value will be reported.

Supporting analysis of the primary endpoints will also be performed using m-NRI based on the PP population.

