#### **6. RANDOMIZATION**

IWRS will be used for randomization. The randomization scheme will be reviewed and approved by a member of the sponsor's Biostatistics and Data Management (BDM) group or designee. The sites will randomize eligible subjects by contacting IWRS at Visit 2 after all the relevant Baseline

procedures are completed and assessed as appropriate. A subject who fulfills the study eligibility requirements will be randomly assigned to treatment. The randomization will be stratified by prior biologic use.

The IWRS will assign a randomization number to the subject, which will be used to link the subject to the treatment group and will specify a unique Blister Wallet IP kit number for the IP to be dispensed to the subject at Visit 2 for the Titration Period. The sites will log in to IWRS during each subsequent subject visit to obtain the kit numbers of the Bottle Kits to be dispensed at study Visits 3-7.

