### Multiple Imputation procedures for missing PASI scores:

Intermittent missing values of PASI scores will be imputed separately for each treatment group using the Markov Chain Monte Carlo (MCMC) method, generating 50 copies of the imputed dataset with monotonic missing pattern. For each of the 50 datasets, missing values at scheduled visits (Weeks 4, 8, 12, 16, 20 and 24) will be imputed using a linear regression model. The imputations will include the following variables: baseline BMI, baseline PASI score, and PASI scores at the previous scheduled visits. SAS Proc MI will be used. Imputed PASI-75 response (Yes/No) will be derived for each imputed dataset.

Example SAS code is as follows:

```
PROC MI DATA = PASI1 OUT = PASI2 SEED = 132138 NIMPUTE = 50 NOPRINT;  
BY TRT01PN;
```

```
MCMC IMPUTE = MONOTONE;  
VAR BASEBMI BASEPASI _3 _4 _5 _6 _7 _8;  
RUN;  
  
PROC MI DATA = PASI2 OUT= PASI3 SEED = 132138 NIMPUTE = 1 NOPRINT;  
BY TRT01PN _IMPUTATION_;  
MONOTONE REGRESSION;  
VAR BASEBMI BASEPASI _3 _4 _5 _6 _7 _8;  
RUN;
```

Multiple Imputation procedures for missing IGA scores:

The imputation of post-baseline IGA scores will be performed following a similar approach as described for PASI scores. Intermittent missing IGA scores will be imputed separately for each treatment group using the Markov Chain Monte Carlo (MCMC) method where 50 copies of the dataset with monotonic missing pattern will be generated. For each of the 50 datasets, missing values at scheduled visits (Weeks 4, 8, 12, 16, 20 and 24) will be imputed using a logistic regression model including baseline BMI, baseline IGA score, and IGA scores at the previous scheduled visits. SAS Proc MI using the logistic regression method for monotone data will be used for the imputation. IGA Treatment Success status (Yes/No) will then be derived for each imputed dataset.

Example SAS code is as follows:

```
PROC MI DATA = IGA1 OUT = IGA2 SEED = 132138 NIMPUTE = 50 NOPRINT;  
BY TRT01PN;  
MCMC IMPUTE = MONOTONE;  
VAR BASEBMI _3 _4 _5 _6 _7 _8;  
RUN;  
  
PROC MI DATA = IGA2 OUT= IGA3 SEED = 132138 NIMPUTE = 1 NOPRINT;  
BY TRT01PN _IMPUTATION_;  
MONOTONE LOGISTIC;  
VAR BASEBMI _3 _4 _5 _6 _7 _8;  
RUN;
```

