### **12.3 Demographic and Baseline Characteristics**

Demographics and baseline characteristics will be summarized overall and by treatment for the FAS, PP and Safety populations. The following demographic and baseline variables will be included:

- Age
- Gender
- Race
- Ethnicity
- Weight
- Height
- Waist circumference
- BMI
- Baseline PASI score
- Baseline BSA
- Baseline IGA

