### **12.8.2 Secondary Efficacy Analyses**

All secondary efficacy analyses will be performed on the FAS and PP populations.

The following categorical secondary efficacy endpoints will be summarized using the number and percentage of subjects within each category for each treatment group. A same logistic regression model as used for the primary endpoint will be performed. Each PPC-06 group will be compared to placebo separately as described in the primary analysis.

- Proportion of subjects who achieve PASI-50 and PASI-75 by visit in the Double-Blind Treatment Period
- Proportion of subjects who achieve an IGA score of clear or almost clear by visit in the Double-Blind Treatment Period

The observed values and change from baseline in PP PGA will be summarized as categorical endpoint using frequency counts and percentages. The change from baseline in severity categories will be compared between treatment groups using a Wilcoxon rank sum test.

The following continuous secondary efficacy endpoints will be summarized descriptively and analyzed using an Analysis of Covariance (ANCOVA) including factors for treatment, baseline

BMI, and pooled analysis center. Each PPC-06 group will be compared to placebo separately. The least square mean (LSM) difference, along with the 95% CI and p-value will be reported.

- Change from Baseline and percent change from Baseline in total PASI Score by visit in the Double-Blind Treatment Period
- Change from Baseline and percent change from Baseline in percent of affected BSA by Visit in the Double-Blind Treatment Period
- For applicable subjects, change from baseline in NAPSI of the target fingernail at Weeks 12, 16 and 24
- For applicable subjects, change from baseline by visit in PSSI in the Double-Blind Treatment Period
- Change from Baseline and percent change from Baseline in pruritus NRS score by Visit in the Double-Blind Treatment Period

The following time to event variables will be analyzed using the Kaplan-Meier (KM) method. Subjects who have not achieved treatment response by the last visit or discontinue the study will be censored at their last visit. The mean, 25th, 50th, and 75th percentile time to achieving a treatment success will be reported; log-rank test will be performed for the comparison between each PPC-06 arm and placebo.

- Time to achieving PASI-75 response
- Time to achieving IGA 0 or 1

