### **12.8.4 Subgroup Analyses**

The co-primary efficacy endpoints will be analyzed for the following subgroups:

- Baseline hsCRP (< 5 mg/L, >=5 mg/L)
- Baseline BMI (<30, >=30)
- Occurrence of diarrhea (Subjects reported diarrhea as adverse event by Week 24, subject did not report diarrhea by Week 24)

The same method as described in [Section 12.8.1](#) will be used for the subgroup analyses, except that no formal hypothesis testing will be performed.

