	PPC-06 400 mg QD (N=XX)	PPC-06 400 mg BID (N=XX)	PPC-06 600 mg BID (N=XX)	Placebo (N=XX)
Pooled Analysis Site (Clinical Sites)				
A01 (112 113 114)				
N	XX	XX	XX	XX
Response Rate [1]	XX.X	XX.X	XX.X	XX.X
A02 (101 102 105)				
N	XX	XX	XX	XX
Response Rate [1]	XX.X	XX.X	XX.X	XX.X
XXX				
N	XX	XX	XX	XX
Response Rate [1]	XX.X	XX.X	XX.X	XX.X

<include all pooled *Analysis Site*>

Note: PASI=Psoriasis Area and Severity Index. PASI-75 Response is defined as achieving a reduction of 75% or greater from Baseline.

[1] Average PASI-75 response rate over 50 imputed datasets.

Generated on XX/XX/XX:XXXX by XXXXX / Uses: XXXX / Reference: Listing XXXX

<Repeat for>

Table 14.2.1.5.2: Analysis of Co-Primary Efficacy Outcome  
IGA Treatment Success Rate at Week 24 by Visit and Analysis Sites  
Full Analysis Set, Multiple Imputation

*Programming note: modify the Note accordingly for the definition of IGA treatment success*

Table 14.2.2.1.1.1: Analysis of Secondary Efficacy Outcome  
 Change from Baseline in Total PASI Score by Visit  
 Double-Blind Treatment Period  
 Full Analysis Set, Multiple Imputation

	PPC-06 400 mg QD (N=XX)	PPC-06 400 mg BID (N=XX)	PPC-06 600 mg BID (N=XX)	Placebo (N=XX)
Week 8				
Change from baseline [1]				
N	XX	XX	XX	XX
Mean	XX.X	XX.X	XX.X	XX.X
Analysis of Covariance (ANCOVA) [2]				
LSM (SE)	XX.X (XX.X)	XX.X (XX.X)	XX.X (XX.X)	XX.X (XX.X)
LSM, 95% CI	XX.X, XX.X	XX.X, XX.X	XX.X, XX.X	XX.X, XX.X
LSM Difference (SE), PPC-06 vs. Placebo	XX.X (XX.X)	XX.X (XX.X)	XX.X (XX.X)	
95% CI	XX.X, XX.X	XX.X, XX.X	XX.X, XX.X	
p-value	X.XXXX	X.XXXX	X.XXXX	

<Repeat for other visits: Week 12, Week 16, Week 20, and Week 24>

Note: PASI=Psoriasis Area and Severity Index, SE=Standard Error.

[1] Average based on 50 imputed datasets.

[2] ANCOVA model includes treatment as factor, baseline BMI and pooled analysis centers as covariates.

Generated on XX/XX/XX:XXXX by XXXXX / Uses: XXXX / Reference: Listings XXXX

<Repeat for>

Table 14.2.2.1.1.2: Analysis of Secondary Efficacy Outcome  
Percent Change from Baseline in Total PASI Score by Visit  
Double-Blind Treatment Period  
Full Analysis Set, Multiple Imputation

Table 14.2.2.1.2.1: Analysis of Secondary Efficacy Outcome  
Change from Baseline in Total PASI Score by Visit  
Double-Blind Treatment Period  
Full Analysis Set, LOCF

	PPC-06 400 mg QD (N=XX)	PPC-06 400 mg BID (N=XX)	PPC-06 600 mg BID (N=XX)	Placebo (N=XX)
Baseline				
N	XX	XX	XX	XX

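### The only randomisation stratum is in no analysis or imputation model, and the change-score ANCOVAs omit the outcome's own baseline value

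*SAP*

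**What the plan says.** On allocation, SAP section 6 (and protocol section 6.6.1) states: "The randomization will be stratified by prior biologic use". No other stratification factor is named.

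The models then use other terms:

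- **Co-primary endpoints (SAP 12.8.1):** "Each multiple imputed dataset will be analyzed using a logistic regression model with treatment group, baseline BMI, and pooled analysis center as factors". SAP 12.8.2 reuses this model for the by-visit responder endpoints.
- **Continuous secondary endpoints (SAP 12.8.2):** these are "analyzed using an Analysis of Covariance (ANCOVA) including factors for treatment, baseline" BMI and pooled centre. The table shells repeat it: "ANCOVA model includes treatment as factor, baseline BMI and pooled analysis centers as covariates". Five endpoints are covered (PASI, BSA, NAPSI, PSSI, pruritus NRS). PASI, BSA and NRS are each analysed as change and as percent change, so there are 3 × 2 + 2 = 8 ANCOVA outcomes.
- **Imputation (SAP section 9):** PASI is imputed by arm from BMI, baseline PASI and earlier PASI. Missing IGA scores are to be "imputed using a logistic regression model including baseline BMI, baseline IGA score, and IGA scores at the previous scheduled visits", but both example IGA blocks have "VAR BASEBMI _3 _4 _5 _6 _7 _8", with no baseline IGA. The PASI blocks do list baseline PASI.

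Prior biologic use is also absent from the list in SAP 12.3 ("The following demographic and baseline variables will be included") and from the list in SAP 12.8.4 ("The co-primary efficacy endpoints will be analyzed for the following subgroups"), which has only hsCRP, BMI and diarrhoea. Protocol 8.7.1 leaves room for further model terms, and protocol 8.1 offers prior biologic use as its example subgroup. The SAP takes up neither, and protocol 8.10 gives the SAP precedence.

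**The concern.** A factor judged important enough to stratify on would normally be in the analysis model, and a change-score ANCOVA would normally carry the baseline value of its outcome. Here the analysis does neither, although the variables are already to hand.

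What is at stake differs by model. In the logistic models, leaving out prognostic covariates pulls the odds ratio toward 1 and loses a little power; the standard error of the log odds ratio is not inflated. In the absolute-change ANCOVAs, a chance imbalance at baseline stays in the treatment contrast, and residual variance is usually larger than it need be. The IGA mismatch is of another kind: the text and the code for a co-primary endpoint specify different imputation models.

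**Working it through.** **Inputs from the documents.** Response 15% v 45%, two-sided 0.05, 100 randomised and about 50 completers per arm (SAP section 7); at most 30% with prior biologic use (protocol 5.3, note 2 to exclusion 4).

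**Assumed, because the documents give no figures.** All prognostic odds ratios, the baseline to Week 24 correlation ρ, the SD ratio k = SD(Week 24)/SD(baseline), six pooled centres, and prevalence at the 30% cap.

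**1. The plan's power.** With pooled variance under the null and 50 per arm:

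Φ{[0.30 − 1.96·√(2·0.30·0.70/50)] / √[(0.15·0.85 + 0.45·0.55)/50]} = Φ(0.1204/0.0866) = Φ(1.39) = 0.918.

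Two independent endpoints give 0.9177² = 0.842, which matches the stated 84%. That figure uses no covariates and is not in dispute.

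**2. Co-primary logistic model.** Simulation with 10,000 two-arm trials per scenario, 50 per arm, the stratum balanced across arms, intercepts set to give 15% and 45% marginally, Wald test, no missing data. Power per endpoint (Monte Carlo SE about 0.3 points):

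| Assumed effects | As planned | + stratum | + stratum and severity |
|---|---|---|---|
| Strong: OR 0.4 stratum, 0.5 per SD severity | 91.6% | 92.1% | 93.6% |
| Mild: OR 0.6, 0.7 per SD | 91.0% | 91.4% | 91.8% |
| Baseline IGA 4 v 3: OR 0.4, 25% severe | 91.4% | 92.0% | 92.4% |
| Not prognostic | 91.8% | 92.0% | 91.9% |

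- The full adjustment gains 2.0, 0.8 and 1.0 points in the first three rows and loses nothing in the last.
- At 100 per arm, power is 99.6% to 99.8% either way. The imputed full analysis set lies between 50 and 100 per arm.
- Median SE of the log odds ratio, strong case: 0.530, 0.545, 0.595. It rises with adjustment.
- Null rejection, strong case: 4.5%, 4.9%, 5.0% (Monte Carlo SE 0.2).
- Marginal odds ratio: (0.45/0.55)/(0.15/0.85) = 4.64. The matching conditional values are 5.54 (strong), 4.89 (mild) and 5.04 (IGA).

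A second simulation adding the stratum alone to a treatment-only model (4,000 trials per setting, stratum odds ratio 1 down to 0.2) gave gains of about 0.5 to 1.4 points at 50 per arm and almost none at 100.

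**3. Absolute-change ANCOVA.** Residual variance with the baseline value, relative to without it:

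k²(1 − ρ²)/(1 + k² − 2ρk), which is (1 + ρ)/2 at k = 1.

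| k | ρ = 0.3 | ρ = 0.5 | ρ = 0.7 |
|---|---|---|---|
| 0.75 | 0.46 | 0.52 | 0.56 |
| 1 | 0.65 | 0.75 | 0.85 |
| 1.5 | 0.87 | 0.96 | 1.00 |
| 2 | 0.96 | 1.00 | 0.93 |

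In large samples the ratio cannot exceed 1. At k = 1, a comparison with 80% power on the unadjusted change would have Φ[(1.96 + 0.842)/√ratio − 1.96] = 93.5%, 90% and 86%.

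**4. Chance imbalance.** A one-SE baseline difference at 50 per arm is √(2/50) = 0.20 SD. It shifts the unadjusted change contrast by (1 − ρk)·0.20 SD. At k = 1 this is 0.14, 0.10 and 0.06 SD for ρ = 0.3, 0.5 and 0.7; at k = 2, ρ = 0.5 it is zero.

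Steps 3 and 4 apply to absolute change only. For percent change the gain is zero if percent change is unrelated to baseline.

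**The case against.** The strongest objection is that the stratum barely matters for the primary analysis. Its own contribution in step 2 is 0.4 to 0.6 points where it is prognostic, close to Monte Carlo error, and a four-arm run with 6 or 15 centres gave 0.0 to 0.5 points with null rejection near 5%. That stands: for the co-primary endpoints this is a matter of consistency and slight efficiency.

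Other points also have force:

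- PASI-75 is a dichotomised percent change, so baseline PASI may not predict it. The 2.0-point gain depends on an assumed severity effect.
- The gap between 4.64 and 5.54 is a marginal against a conditional odds ratio, not a bias.
- The main benefit falls on secondary endpoints in a Phase 2 trial with no multiplicity control over them.
- Prevalence could be below the 30% cap, though the pattern is the same at 15%.
- The imputation runs by arm. With about 50 completers, at most about 0.30 × 50 = 15 would be in the stratum, and sparse cells in the IGA imputation model were not tested.
- Protocol 8.4 lets imbalanced baseline variables enter as covariates. That is optional, confined to exploratory analyses, and decided after the imbalance is seen, so it only partly answers the point.
- Prior psoriasis treatments do appear in by-subject listings (SAP 12.6).
- The IGA code is labelled as an example and is a separate matter. It still contradicts the text.

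None of this argues for leaving the covariates out.

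**Conclusion.** The concern holds on all three points, as an improvement that should be made rather than a defect that threatens validity. Type I error is sound and the 84% power is reproduced.

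For the co-primary endpoints, the expected gain from stratum plus severity is 0.8 to 2.0 power points per endpoint at 50 per arm if the covariates are prognostic to the assumed degree. It is nil if they are not, and close to nil at 100 per arm. For absolute change, the cut in residual variance is 15% to 35% at equal SDs and between none and 54% over the wider range shown, with protection from chance baseline imbalance in most of those cases. All of these sizes rest on assumed effects, correlations and SD ratios, and on simulations without missing data. The IGA text and code mismatch is a plain inconsistency; its numerical effect was not estimated.

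**What to change.** Before unblinding, amend the SAP as follows:

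1. Add prior biologic use (yes/no, as randomised) to the logistic, ANCOVA and imputation models. State in advance what will be done if sparse cells stop the by-arm IGA imputation model from fitting.
2. Add baseline PASI to the PASI-75 and PASI-50 models and baseline IGA (3 v 4) to the IGA model. Note that the reported odds ratios are then conditional on these terms.
3. Add the matching baseline value to each ANCOVA in section 12.8.2, and update the shell footnotes.
4. Put baseline IGA in the variable list of both IGA imputation blocks, as the section 9 text already requires.
5. List prior biologic use in the baseline characteristics table (section 12.3).

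The cost is SAP wording and code, plus one degree of freedom per added term. The stratum is held in the IWRS and the baseline scores are already collected, so no new data are needed.

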### **12.8.2 Secondary Efficacy Analyses**

All secondary efficacy analyses will be performed on the FAS and PP populations.

The following categorical secondary efficacy endpoints will be summarized using the number and percentage of subjects within each category for each treatment group. A same logistic regression model as used for the primary endpoint will be performed. Each PPC-06 group will be compared to placebo separately as described in the primary analysis.

- Proportion of subjects who achieve PASI-50 and PASI-75 by visit in the Double-Blind Treatment Period
- Proportion of subjects who achieve an IGA score of clear or almost clear by visit in the Double-Blind Treatment Period

The observed values and change from baseline in PP PGA will be summarized as categorical endpoint using frequency counts and percentages. The change from baseline in severity categories will be compared between treatment groups using a Wilcoxon rank sum test.

The following continuous secondary efficacy endpoints will be summarized descriptively and analyzed using an Analysis of Covariance (ANCOVA) including factors for treatment, baseline

BMI, and pooled analysis center. Each PPC-06 group will be compared to placebo separately. The least square mean (LSM) difference, along with the 95% CI and p-value will be reported.

- Change from Baseline and percent change from Baseline in total PASI Score by visit in the Double-Blind Treatment Period
- Change from Baseline and percent change from Baseline in percent of affected BSA by Visit in the Double-Blind Treatment Period
- For applicable subjects, change from baseline in NAPSI of the target fingernail at Weeks 12, 16 and 24
- For applicable subjects, change from baseline by visit in PSSI in the Double-Blind Treatment Period
- Change from Baseline and percent change from Baseline in pruritus NRS score by Visit in the Double-Blind Treatment Period

The following time to event variables will be analyzed using the Kaplan-Meier (KM) method. Subjects who have not achieved treatment response by the last visit or discontinue the study will be censored at their last visit. The mean, 25th, 50th, and 75th percentile time to achieving a treatment success will be reported; log-rank test will be performed for the comparison between each PPC-06 arm and placebo.

- Time to achieving PASI-75 response
- Time to achieving IGA 0 or 1

